15.9 Analysis of unit level microbiological data

Incidence of microbiological outcomes will first be described as the number and proportion of patients within each of the five ecology periods (pre-trial, period 1, washout, period 2 and post-trial).

This will be done according to the randomisation sequence, that is, separately for sites randomised to control \rightarrow SDD and sites randomised to SDD \rightarrow Control.

The main hypothesis to be tested is whether rates are the same with and without the SDD intervention. This will be assessed using a non-inferiority comparison and with a non-inferiority margin set at 2%.

To 'declare' non-inferiority of SDD compared to usual care, the upper bound of the 95% confidence interval around the absolute risk difference (SDD - usual care) will need to be lower than 2%.

We will analyse data from all 5 periods using linear regression to model the proportion of events in each cluster and each period.

To test whether the proportion of patients with the SDD intervention is non-inferior to the one with usual care, we will group periods 2 and 3 and, within each arm (SDD or usual care), will estimate the change between period 1 (baseline) and periods 2/3 combined.

We will then estimate the difference (SDD – Usual care) in change from baseline to assess whether the change with SDD is similar (non-inferior) to the change with usual care.

Using the same model, to further assess the effect of SDD over time including potential withdrawal effects (i.e. whether rates change after withdrawing SDD), we will compare the change between period 3 and periods 4/5 combined in units randomised to use SDD in the first intervention period.

16 Health economics evaluation: Australia

There will be a separate cost-effectiveness and cost-utility analysis that will use the most appropriate data collected across all settings but will use parameters that are judged context-specific (e.g. unit costs) and taken from local sources.

All health economic analyses will be undertaken from the perspective of the "idealized insurer"/third party payer (i.e. the provincial, state and federal government payer perspective in Australia). In Australia these data will be obtained through routine patient follow up and augmented through data linkage via the Centre for Health Records Linkage to capture hospitalisations and Medicare Australia to capture pharmaceutical and medical service use.

17 Study compliance

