3.2.4 A cluster-RCT of SDD

Our preparatory studies indicated that a high-quality comparative effectiveness study of SDD, including a study of the ecology of infection and microbial resistance is acceptable, necessary and feasible.

SDD is both an individual patient-based intervention and an ecological intervention. It may have direct individual patient-centred effects and reduces the carriage of potentially pathogenic microorganisms that may lead to a hospital acquired infection. SDD may also alter the ecology of a unit and may have indirect effects both among patients receiving SDD but also in those patients in the unit not receiving the intervention.

Individual patient randomisation, as opposed to unit randomisation will not replicate the manner in which SDD would subsequently be deployed in practice and will have a large risk of failing to adequately evaluate the influence of SDD on antibiotic resistance. For the prophylaxis to be maximally effective it should be introduced as soon as possible after ICU admission - this is only feasible in a cluster design where the prophylactic SDD regime becomes the participating ICUs standard practice for the trial period.

Originally planned as an international, multi-centred, cluster RCT that was to be simultaneously conducted in Canada, UK, Australia and New Zealand and designed using metrics from these countries to determine a 3.5% absolute reduction in hospital mortality and a 2% non-inferiority increase in antibiotic resistance, a study population of 22500 patients from 100 clusters (ICUs) was projected. This international trial was dependent on success in simultaneous applications to national research funding agencies in the four countries.

Only the Australian NHMRC grant application was successful and in 2014 a decision was made to modify the original cluster RCT to a crossover-cRCT (x-cRCT) with the George Institute for Global Health acting as Principal Sponsor in 2014. The x-cRCT design is consistent with the aims of the original cRCT and allows each ICU to serve as its own control, minimising the risk of imbalance between participating ICUs, and significantly increasing statistical power compared to a parallel group cRCT.¹⁹

The ecological assessment was modified to an observational study to determine secular trends in antibiotic resistance patterns before, during, in between and after the intervention periods.

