5.2 Secondary outcomes

5.2.1 Microbiological assessments

- 1. The incidence of antibiotic resistant organisms (AROs) isolated from all clinical and surveillance specimens, including the incidence of AROs in cultures from blood or other sterile sites, the incidence of AROs in non-sterile clinical and surveillance specimens, and the incidence of bacteraemia in all blood culture specimens
- 2. Changes in ARO rates between surveillance, intervention and post intervention periods
- 3. The incidence of Clostridioides difficile infections
- 4. Total antibiotic usage (as daily defined doses)

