8.6 Ecology (microbiology) surveillance periods

During the fifteen discrete ecology (microbiology) surveillance periods (three pre-trial, three during the last 3-months of each intervention period, three during the inter-period gap and three post-trial), data will be collected on all patients admitted to the ICU during one full week of each calendar month of the periods regardless of mechanical ventilation status.

Demographics, diagnosis and severity of illness score will be documented, the presence and duration of mechanical ventilation, the ICU and hospital length of stay and hospital mortality.

Microbiology results will be collected documenting any positive test for *Clostridioides difficile*, the results of all blood cultures and any positive AROs in sterile or non-sterile sites.

9 Study timelines

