15.2.1 Level of statistical significance

One interim analysis is planned once 100% of Australian sites have finished recruitment to the first 12-month intervention period.

Haybittle-Peto stopping rules will be used at the interim analysis using a difference of 3 standard-deviations on hospital mortality (or a p-value of 0.0027).

Given the conservative rule used and the negligible amount of type-I error rate spent at the interim analysis, the significance threshold will remain at 5% for the final analysis.

Final analyses of the primary outcome including sensitivity analyses will all be conducted using a two-sided significance level of 5%.

For the four secondary clinical outcomes, we will control the family-wise error rate by applying a Holm-Bonferroni correction.

No multiplicity correction will be applied to the ecology analyses or other statistical tests.

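### Section 15.9 states one 2-point absolute non-inferiority rule for microbiological outcomes generally, although 2% was set for antibiotic resistance; as worded it also reaches rarer harms such as C. difficile

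*Protocol*

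**What the plan says.** Section 15.9 of the protocol begins: "Incidence of microbiological outcomes will first be described as the number and proportion of patients within each of the five ecology periods". The main hypothesis follows without a narrower subject, and is tested for non-inferiority "with a non-inferiority margin set at 2" per cent. Non-inferiority is declared on one condition: "the upper bound of the 95% confidence interval around the absolute risk difference (SDD - usual care) will need to be lower than 2" per cent. No outcome is named and no outcome-specific margin is given. The section then defines the contrast as a difference between arms in the change from the pre-trial period to the next two periods combined.

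Elsewhere the protocol shows what the microbiological outcomes are. Section 5.2.1 lists "The incidence of Clostridioides difficile infections" among them, and section 15.7.1 lists new AROs, new bloodstream infections and new C. difficile infections. Section 8.6 collects all three kinds of result in the ecology periods, including C. difficile: "Microbiology results will be collected documenting any positive test for" that organism.

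The figure of 2% appears in one other place. Section 3.2.4, on the original parallel cluster design, refers to "a 2% non-inferiority increase in antibiotic resistance". Section 15.2.1 adds: "No multiplicity correction will be applied to the ecology analyses or other statistical tests".

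**The concern.** An absolute margin has a clinical meaning only relative to the rate it is applied to. Two points on a common outcome is a small relative change. On a rare one it can be a multiple of the background rate. The protocol attaches 2% to antibiotic resistance when it gives the figure a purpose, then states it in 15.9 under wording that takes in rarer events, without giving a reason.

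What is at stake is the formal label. The trial seeks a mortality benefit without ecological harm. Section 3.1 links broad-spectrum antibiotics to C. difficile, and section 10.6 has every C. difficile case reported as a serious adverse event. A declaration of non-inferiority that is compatible with a doubled rate of such an event would be weak evidence presented as a positive finding.

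**Working it through.** **The plan's own figure.** No sample size, power or base rate is stated for the non-inferiority test. The nearest design figure is the 4.2% detectable mortality difference (section 15.1: 20 clusters, 150 patients per period, control mortality 29%, ICC 0.01, inter-period correlation 0.005, 80% power). The design effect is 1 + 149 × 0.01 − 150 × 0.005 = 1.74. The effective size per arm is 3,000 / 1.74 ≈ 1,724, and the detectable difference is 4.23%. The figure reproduces.

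**What the margin allows.** The largest risk ratio inside a 2-point margin at control rate p is (p + 0.02) / p:
- p = 0.25%: 9
- p = 0.5%: 5
- p = 1%: 3
- p = 2%: 2
- p = 20%: 1.1

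**Sample size (assumed).** The ecology data come from one week per month for three months per period, so 3 of 52 weeks. Section 15.1 gives 150 to 250 patients per ICU per period, section 3.2.3 gives 36.4% of ICU admissions as eligible, and there are 19 to 29 ICUs.
- Low: 150 / 0.364 × 3/52 × 19 ≈ 450
- High: 250 / 0.364 × 3/52 × 29 ≈ 1,150

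These are per-arm numbers for a simple comparison over both intervention periods. For the contrast in 15.9, each arm is half the ICUs over two post-baseline periods, which gives the same n, with a one-period baseline n₀ = n/2 (225 to 575).

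**Chance of declaring non-inferiority when the rate truly doubles.** The true difference is d = p, and the declaration requires the upper 95% limit to be below 0.02:

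P = Φ((0.02 − d) / SE − 1.96)

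- Simple comparison: SE² = D × [p(1−p) + 2p(1−2p)] / n
- Difference in change: SE² = D × {[p(1−p) + 2p(1−2p)] / n + 2p(1−p) / n₀}

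D is a design effect, taken as 1.0 to 1.5. The doubling is assumed to last through both post-baseline periods, and no credit is taken for within-ICU correlation over time.

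Example, difference in change, p = 0.5%, n = 1,150, n₀ = 575, D = 1.0: SE² = 0.014875/1,150 + 0.00995/575 = 0.0000302, so SE = 0.0055. Then 0.015/0.0055 − 1.96 ≈ 0.77 and P ≈ 78%. With n = 450, n₀ = 225 and D = 1.5, SE = 0.0108 and P ≈ 29%.

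| Assumed control rate | Difference in change (15.9) | Simple comparison of arms |
|---|---|---|
| 0.25% | 63-99% | 94% to over 99% |
| 0.5% | 29-78% | 57-99% |
| 1% | 10-25% | 17-51% |
| 2% | 2.5% | 2.5% |

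At 2% a doubling lies exactly on the margin, so the chance equals the one-sided error of the rule. The normal approximation is rough at the lowest rates, where only a few events are expected per arm.

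**The case against.** The best reply is that 15.9 never names C. difficile or bloodstream infection. Its test concerns changes in rates across pre-trial, intervention, washout and post-trial periods. That closely matches the secondary outcome on changes in ARO rates (5.2.1, item 2) and the secondary analysis in 15.2.2. With 3.2.4 tying 2% to resistance, the rule can be read as an ARO rule already, and the statistical analysis plan may say so. This stands in part: the reach to C. difficile is inferred from general wording, and a reader should not say the protocol explicitly sets a C. difficile margin. But the opening subject of 15.9 is plural and unrestricted, and C. difficile is collected in exactly these periods. A rule this definite should state its scope.

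A second reply is that these harms are examined elsewhere. Section 15.7.1 compares them between arms with no margin, and serious adverse events are compared under 15.8. This stands. A reader might infer that a doubling would go unseen, and the protocol does not support that.

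A third reply is that the size depends on an assumed rate and on the contrast. This also stands. A reader might infer that passing is close to automatic at 1%, or that a tripling from 1% would pass. Under 15.9 a doubling at 1% passes only 10-25% of the time, and a tripling from 1% sits on the margin and passes 2.5% of the time.

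**Conclusion.** The point holds as a defect of scope in the 15.9 declaration. One absolute margin, with a stated origin only in antibiotic resistance, is worded to cover outcomes for which it may be far too wide. How wide depends on a C. difficile rate that the protocol does not give. If the control rate is 0.5% or lower, a true doubling would be labelled non-inferior with a probability of 29-78% or more under the specified contrast. At 1% that probability is 10-25%, still well above the 2.5% that the rule implies at its margin. At 2% there is no excess. These figures rest on the assumed surveillance-week samples, a design effect of 1.0 to 1.5 and a normal approximation. No calculation is offered for bloodstream infection. It is included because the same wording reaches it and the protocol gives no reason for a 2-point margin there. The primary outcome and the comparisons in 15.7.1 are unaffected.

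**What to change.** State in 15.9, and carry into the statistical analysis plan, that the 2% non-inferiority declaration applies to the ARO outcome only. For C. difficile and bloodstream infection, report in the same analysis the risk difference and risk ratio with 95% confidence intervals, with no non-inferiority declaration. This takes about one sentence and changes no data collection, sample size or primary analysis. The cost is that no formal non-inferiority claim can be made for those two outcomes.

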3.2.3 Inception cohort pilot study

We conducted an inception cohort pilot study in five centres in Australia, New Zealand, United Kingdom, Canada and the USA to determine the number of ICU patients eligible for the present study, to describe the baseline characteristics of the study population, to establish the duration of study treatment that would be required and to prospectively determine the in-hospital mortality rate for the study population.

We established that 36.4% (95%CI 32.6% to 40.2%) of all patients admitted to the five ICUs met the inclusion criteria for the planned RCT and the average duration of study treatment would be 7.8 days (95%CI 7.1 to 8.6 days). The hospital mortality rate was 29.9% (95%CI 23.7 to 36.0%). 61% of patients were already being prescribed therapeutic antibiotics at the time of ICU admission. The potential duration of therapy for patients identified as fulfilling the study eligibility criteria was 10 days. The time to first dose of trial intervention was 4.5 hours.

A second pilot study of the delivery of the intervention has been completed in one centre in Canada. It demonstrated a very high fidelity of delivery of the intravenous and oral/gastric intervention (>90%) and concluded the intervention delivery for a cluster-RCT (cRCT) was feasible.

To address the question of whether or not to include the intravenous component of SDD, we conducted a comparative cohort study of patterns and outcomes from infection in ICUs using SDD in the UK. After adjustment for severity of illness and unit-level random effects, there were no statistically significant differences in mortality, but a lower rate of ICU-acquired infections in SDD units that used an IV antimicrobial component (OR 0.09, 95%CI 0.01 to 0.63, p=0.015).

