6.4 Ecology surveillance period eligibility criteria

6.4.1 Inclusion

1. All patients admitted to the ICUs regardless of ventilation status, during one full week of every calendar month for 3-months during the pre-trial period, during one week of each

month of the final 3-months of the two interventional periods, the inter-period gap and post-trial periods for the duration of their ICU admissions.

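### The 2% resistance non-inferiority test subtracts a three-week pre-trial baseline in full instead of adjusting for it, which costs precision by an amount that depends on a resistance ICC/IPC the protocol does not give

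*Protocol*

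**What the plan says.** Protocol section 15.9 lists five ecology periods (pre-trial, first intervention, washout, second intervention, post-trial) and uses "linear regression to model the proportion of events in each cluster and each period". For the non-inferiority test it groups the second and third of these and, within each arm, "will estimate the change between period 1 (baseline) and periods 2/3 combined". It then takes the SDD minus usual-care difference "in change from baseline to assess whether the change with SDD is similar (non-inferior) to the change with usual care". To declare non-inferiority, "the upper bound of the 95% confidence interval around the absolute risk difference (SDD - usual care) will need to be lower than 2" per cent. No baseline covariate is named, and nothing says that the two sequences share a common pre-trial mean.

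The baseline is short. Section 6.4.1 collects it on all ICU patients "during one full week of every calendar month for 3-months during the pre-trial period". Section 8.6 gives three such weeks to each of the five periods.

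Section 15.1 gives an ICC and an IPC for mortality. The protocol gives none for resistance, no expected resistance prevalence and no power figure for this test.

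**The concern.** The outcome is measured in every ICU before randomised treatment starts. Because ICUs are randomised, pre-trial proportions have the same expectation in both sequences, so the baseline is not needed to remove bias. Its only use is to gain precision. Subtraction gives it a fixed weight of 1, whereas the best weight is the regression slope of the follow-up proportion on the baseline proportion. A proportion based on a few dozen patients is noisy, so that slope can be well under 1, and full subtraction then carries the noise into the contrast.

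The verdict turns on one confidence limit. An interval wider than the data require makes an inconclusive result more likely when SDD has no effect on resistance. Section 4.1 puts not increasing resistance into the trial's aim, and 15.9 holds the only margin-based test of it.

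**Working it through.** **The plan's own figure.** The 15.1 table concerns mortality, but it confirms how the ICC and IPC are used. With ICC 0.01, IPC 0.005 and 150 patients per cluster-period, the design effect is 1 + 149 × 0.01 − 150 × 0.005 = 1.74. For 20 clusters, a 29% control rate and 80% power, the detectable reduction is 4.23% against the stated 4.2%. Power at the other tabulated reductions lies within about 2 points of 80%.

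**Baseline size (derived, not stated).** Section 15.1 spans 150 to 250 eligible patients per ICU per 12 months. On eligibility, section 3.2.3 reports: "We established that 36.4% (95%CI 32.6% to 40.2%) of all patients admitted to the five ICUs met the inclusion criteria". New admissions in three weeks are therefore 150/0.364 × 3/52 = 23.8 to 250/0.364 × 3/52 = 39.6. I use m = 24 and m = 40.

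**Variances per ICU, in units of p(1−p).** Let w = IPC and v = (1 − ICC)/m + (ICC − IPC). Each three-week proportion has variance v + w, and any two in the same ICU have covariance w.

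- Subtracted contrast (mean of two follow-up periods minus baseline): v/2 + v = 1.5v
- Best baseline slope: b = w/(v + w)
- Baseline-adjusted contrast: v/2 + w − w²/(v + w)

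Example with ICC 0.01, IPC 0.005 and m = 24: v = 0.99/24 + 0.005 = 0.04625. Subtracted: 0.0694. Adjusted: 0.0231 + 0.005 − 0.0005 = 0.0276. Ratio 2.51, with b = 0.10.

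| ICC / IPC | Source | Best slope (m = 24, 40) | Variance ratio (m = 24, 40) |
|---|---|---|---|
| 0.01 / 0.005 | 15.1, mortality | 0.10, 0.14 | 2.51, 2.33 |
| 0.0093 / 0.0072 | 15.1, mortality | 0.14, 0.21 | 2.34, 2.11 |
| 0.05 / 0.025 | assumed | 0.28, 0.34 | 1.93, 1.79 |
| 0.05 / 0.04 | assumed | 0.45, 0.54 | 1.58, 1.44 |
| 0.10 / 0.08 | assumed | 0.58, 0.65 | 1.39, 1.30 |
| 0.20 / 0.18 | assumed | 0.77, 0.82 | 1.18, 1.14 |

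A simulation at 0.01/0.005 with 20 ICUs and a 10% rate, which includes the cost of estimating the slope, gives ratios of 2.2 to 2.4.

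**Power when SDD has no effect.** SE = √[(1/k₁ + 1/k₂) · p(1−p) · variance] and power = Φ(0.02/SE − 1.96). Prevalence p is assumed. ICUs are taken as equal in size and split as evenly as possible.

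Example with 29 ICUs (15 and 14), p = 2%, m = 24 and 0.01/0.005. Subtracted: SE = √(0.1381 × 0.0196 × 0.0694) = 1.37 points, half-width 2.69, power 31%. Adjusted: SE = 0.865 points, half-width 1.70, power 64% (63% with m unrounded).

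| ICUs | ICC / IPC | Prevalence | Power, m = 24 | Power, m = 40 |
|---|---|---|---|---|
| 29 | 0.01 / 0.005 | 2% | 31% → 64% | 44% → 79% |
| 29 | 0.01 / 0.005 | 5% | 15% → 32% | 21% → 43% |
| 29 | 0.10 / 0.08 | 5% | 13% → 17% | 16% → 20% |
| 29 | 0.20 / 0.18 | 5% | 14% → 16% | 17% → 19% |
| 19 | 0.01 / 0.005 | 2% | 22% → 46% | 31% → 61% |

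In the first row the half-width falls from 2.7 to 1.7 points (m = 24) or from 2.2 to 1.4 (m = 40). An observed difference of exactly zero would fail the 2-point rule under subtraction and pass it under adjustment.

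**The case against.** **The weight of 1 is a reading of the text.** Section 15.9 names a contrast from a regression on all five periods and leaves model details to a separate plan. A model with a common pre-trial mean can also report its effect as a difference in change from baseline. That is fair, but the raw double difference is the more natural reading. A cluster random effect does not alter it: with freely estimated sequence-by-period means and balanced data, the contrast is still the raw difference in changes. Only a baseline covariate or a common baseline mean changes it, and 15.9 names neither.

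**The mortality correlations may not carry over.** This stands. Section 7.7 recommends surveillance swabs without mandating them where they are not usual practice, and it adds swabs in Canada. Detection may therefore differ between ICUs in a lasting way, which would raise the IPC and shrink the penalty. A reader might infer that subtraction doubles the variance whatever the outcome. The documents do not support that, because they give no resistance ICC or IPC.

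**Adjustment does not rescue the test.** This also stands. A reader might infer that subtraction is why the trial could fail to show its resistance aim. Yet even at 0.01/0.005 with 29 ICUs, adjusted power is 32-43% at 5% prevalence and 19-25% at 10%. The margin, the three-week samples and the use of only the first half of the crossover limit it too. Nor is 15.9 the only resistance evidence, since 15.7.1 also compares arms.

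**Small gains do not need high prevalence.** At 5% prevalence and 0.10/0.08 or higher, the gain is already only 2-4 points.

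**Ignoring the baseline is not the remedy.** At 0.10/0.08, subtraction has only 0.63-0.79 of the variance of a follow-up-only analysis. The right comparator is adjustment.

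**Conclusion.** The point holds as an avoidable loss of precision whose size is conditional. As written, 15.9 subtracts a noisy three-week baseline in full, although randomisation makes that unnecessary for bias. The variance ratio against adjustment is 2.1-2.5 at the two mortality ICC/IPC pairs in 15.1, and it falls towards 1.1-1.2 if resistance clusters strongly and persistently by ICU. It stays above 1 throughout the range examined.

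The loss could change the non-inferiority verdict at low prevalence with low correlation. At prevalence of 5% or more, the test stays underpowered under either analysis.

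This rests on the derived 24-40 new admissions per ICU, which does not count patients already in the unit when a surveillance week starts. It also rests on equal ICU sizes, a normal approximation, three-week samples in each period, and assumed prevalence and resistance correlations.

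**What to change.** In 15.9, keep the cluster-period linear regression, the data and the 2% margin, but apply the upper 95% limit to the baseline-adjusted SDD minus usual-care difference. Specify one of two forms:

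- each ICU's pre-trial proportion as a covariate; or
- the pre-trial period kept in the longitudinal model, with one common pre-trial mean for both sequences.

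If the second form is what the present sentence intends, saying so is enough. The cost is a change of wording and about one degree of freedom among 19-29 ICUs. The text should not present this as making the test adequately powered.

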4.2 Design

The SuDDICU trial is an international, multicentre, x-cRCT of eligible patients in participating ICUs using two 12-month interventional trial periods separated by a 3-month inter-period gap.

An observational ecological (microbiological) assessment will be conducted in all ICU patients during one week of each month during the 3-month surveillance period before the first intervention period; in all trial eligible patients during the two 12-month intervention periods; in all ICU patients during one week of each month of the final 3-months of the two intervention periods; in all ICU patients during one week of each month during the 3-month during the 3-month inter-period and post-trial periods.

5 Study outcomes

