7.4 Cessation of treatment

At the end of each 12-month SDD intervention period, patients will continue to receive SDD until they meet criteria for cessation of SDD for a maximum of 90 days, or until the end of the 3-month (90-day) inter-period gap and post-trial period.

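### The SDD-withdrawal contrast in section 15.9 starts from the washout and leaves out the on-SDD period, so it misses any prompt change when SDD stops

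*Protocol*

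**What the plan says.** Protocol section 15.9 first describes microbiological outcomes "within each of the five ecology periods (pre-trial, period 1, washout, period 2 and post-trial", separately for the two randomised sequences. It then fits a linear regression to cluster-by-period proportions from all five periods. For the non-inferiority comparison, in each arm, the model "will estimate the change between period 1 (baseline) and periods 2/3 combined".

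A further use of the same model is to follow the effect of SDD over time, including "potential withdrawal effects (i.e. whether rates change after withdrawing SDD". For this, "we will compare the change between period 3 and periods 4/5 combined in units randomised to use SDD in the first intervention period".

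Three other sections bear on the timing:

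- Section 4.2 gives the layout as "two 12-month interventional trial periods separated by a 3-month inter-period gap".
- Section 8.6 places the surveillance weeks as "three pre-trial, three during the last 3-months of each intervention period, three during the inter-period gap and three post-trial".
- Section 7.4 allows some SDD use to run into the gap: "At the end of each 12-month SDD intervention period, patients will continue to receive SDD until they meet criteria for cessation of SDD", for at most 90 days.

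**The concern.** A withdrawal contrast should span the point at which treatment is withdrawn. In SDD-first units that point lies between period 2 and period 3. The planned contrast begins at period 3, after the unit has stopped starting patients on SDD. A rise or fall in resistance soon after stopping is then already in the reference level and drops out.

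This matters because resistance is part of the trial's aim (section 4.1), and change in resistant-organism rates across surveillance, intervention and post-intervention periods is a named secondary outcome (section 5.2.1). Section 12.2 also justifies the design partly by the ability to study resistance after SDD ceases. This is the only modelled contrast in the protocol aimed at that question. A null estimate could be reported as reassurance that stopping SDD changes nothing, when a prompt change would have been partly or wholly outside the comparison.

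**Working it through.** **Step 1. Number the periods.** Section 15.9 lists five periods in order and its model text calls period 1 the baseline. The numbering is therefore ordinal.

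| No. | Period | SDD-first units | Control-first units |
|---|---|---|---|
| 1 | Pre-trial | off | off |
| 2 | First intervention period | **on** | off |
| 3 | Washout | off, with run-on | off |
| 4 | Second intervention period | off | **on** |
| 5 | Post-trial | off | off, with run-on |

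The same section also calls the two intervention periods period 1 and period 2, so the labels collide.

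**Step 2. Write out the contrasts.** In SDD-first units let the untreated rate be b and the on-SDD rate b + D. Let the washout rate be b + λD and the average rate in periods 4/5 be b + μD. Ignoring secular trend:

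- planned, period 3 to 4/5: (μ − λ)D
- period 2 to period 3: (λ − 1)D
- period 2 to 4/5: (μ − 1)D

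The first two add up to the third. The planned contrast thus omits (λ − 1)D, the change around stopping. With immediate reversal, λ = μ = 0 and the planned contrast is 0 whatever the size of D.

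**Step 3. Size the loss.** The protocol gives no figure for this contrast, so there is none to reproduce, and it does not say how quickly unit ecology reverts. As an assumption, let the effect fade exponentially from month 12 with half-life h, and put τ = h / ln 2. The surveillance months are 9–12 (period 2), 12–15 (period 3), 24–27 (period 4) and 27–30 (period 5). Then

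- λ = τ(1 − e^(−3/τ)) / 3
- μ = τ(e^(−12/τ) − e^(−18/τ)) / 6

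Example, h = 1: τ = 1.443, so λ = 1.443 × (1 − 0.125) / 3 = 0.421 and μ is 0.000 to three decimals. The planned contrast recovers 0.421 of D and the omitted step is 0.579.

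Share of D recovered, sign ignored:

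| h (months) | λ | μ | Planned: 3 v 4/5 | 2 v 4/5 | 2/3 combined v 4/5 | Omitted: 2 v 3 |
|---|---|---|---|---|---|---|
| 0.01 | 0.005 | 0.000 | 0.005 | 1.000 | 0.502 | 0.995 |
| 0.25 | 0.120 | 0.000 | 0.120 | 1.000 | 0.560 | 0.880 |
| 0.5 | 0.237 | 0.000 | 0.237 | 1.000 | 0.618 | 0.763 |
| 1 | 0.421 | 0.000 | 0.421 | 1.000 | 0.710 | 0.579 |
| 3 | 0.721 | 0.034 | 0.688 | 0.966 | 0.827 | 0.279 |
| 6 | 0.845 | 0.180 | 0.665 | 0.820 | 0.742 | 0.155 |
| 12 | 0.918 | 0.423 | 0.496 | 0.577 | 0.537 | 0.082 |

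Averaging period 4 over the whole year (months 15–27) instead lowers the planned column slightly: 0.413 at h = 1, 0.626 at 3, 0.579 at 6 and 0.422 at 12.

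**Step 4. Check the run-on.** Section 3.2.3 gives a mean treatment time of 7.8 days (95% CI 7.1 to 8.6) and a potential duration of 10 days. Assuming exponential durations with mean m, SDD use in the 90-day gap averages m(1 − e^(−90/m)) / 90 of its steady-state level. That is 7.8 / 90 = 8.7% at m = 7.8, 7.9% at 7.1 and 11.1% at 10. The run-on does not make period 3 an on-SDD period.

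**The case against.** The best defence is that the authors treat the washout as part of the SDD era. The non-inferiority contrast groups periods 2 and 3, section 7.4 lets treatment run on, and ecological effects may outlast the drug. On that view, period 3 against 4/5 asks whether rates drift once the SDD era is over, which fits the sentence's wider purpose of following the effect over time. The descriptive summaries by period and sequence will also put period 2 beside period 3.

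Part of this stands. The contrast is informative about slow fading, and a change that begins only after the gap would be captured in full. A reader might infer that the contrast cannot detect any withdrawal effect. The documents do not support that: it is true only under immediate reversal, and with a half-life of 3 to 6 months about two-thirds of the effect would appear. Nor does the 7.8-day mean treatment time show that reversal is fast. It measures drug exposure in patients, not how long unit ecology takes to return.

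A reader might also infer that secular or pandemic-era change will be attributed to withdrawal. Whether the model carries period terms is detail for the SAP, which is not at hand, so this cannot be asserted.

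The defence does not repair the contrast. If the washout belongs to the SDD era, dropping period 2 is inconsistent with the 2/3 grouping used just before. If period 3 is a slip for periods 2/3, the text still needs correcting. A descriptive table is not an estimate with an interval, and no formal contrast spans the on-to-off step.

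**Conclusion.** The point holds. The withdrawal contrast excludes the only on-SDD period in the units it uses, so it misses change that occurs promptly on stopping and captures only later drift. The loss is total under immediate reversal, about 58% at a half-life of 1 month and 28% at 3 months. At longer half-lives the omitted step is smaller: 16% at 6 months and 8% at 12.

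The omission follows directly from the text. The percentages rest on an assumed exponential fade and on the section 8.6 surveillance windows, and the true rate of reversal is unknown.

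This should be fixed but is not critical. It is a follow-on contrast on secondary ecology outcomes, and it does not touch hospital mortality, the sample size or the 2% non-inferiority test.

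**What to change.** In section 15.9:

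1. Number the ecology periods 1 to 5 throughout and stop using period 1 and period 2 for the intervention periods.
2. Make period 2 the on-SDD reference. Estimate the change from period 2 to period 3 in SDD-first units minus the same change in control-first units. The latter are not on SDD in either period, so secular trend common to both sequences is removed.
3. Also estimate the change from period 2 to periods 4/5 in SDD-first units. Label it an uncontrolled before-after change, because control-first units receive SDD in period 4 and cannot serve as an untreated comparator.
4. Keep period 3 against periods 4/5, if wanted, as a measure of late drift.

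Using periods 2/3 combined as the reference would match the non-inferiority contrast, but it is diluted: about 50% recovered under immediate reversal, against 100% with period 2 alone.

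The cost is a short rewording of section 15.9 and the matching contrasts in the SAP. The data are already collected under section 8.6, and no trial procedure changes.
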